Our hypothesis is that micro-dosing with a binary mixture of [¹⁴C]-BaP and another PAH will result in no change in plasma and urine [¹⁴C]-BaP metabolites, the [¹⁴C]-BaP Cmax in blood or the rate of elimination. This hypothesis will be tested by micro-dosing individuals with a binary mixture of [¹⁴C]-BaP and non-radioactive phenanthrene. We will dose individuals with 50 ng of [¹⁴C]-BaP alone and, following a washout period, previously shown to reduce [¹⁴C]-BaP levels in plasma and urine to levels below detection (<1 fg/mL), compare to a binary mixture of 50 ng [¹⁴C]-BaP and 1250 ng of non-labeled phenanthrene (non-carcinogenic PAH²), a BaP:phenanthrene ratio commonly found in food⁵. The determination of the effect of phenanthrene on uptake, metabolism and elimination of [¹⁴C]-BaP will test a basic tenet of the Relative Potency Factor (RPF) approach to risk assessment (proposed by the U.S. EPA) for PAH mixtures⁶, that there is no impact of a PAH on the pharmacokinetics of another PAH (i.e. the cumulative risk is additive).

To date, our accelerator mass spectrometry (AMS) studies with PAHs have employed a single PAH given at a single dose^{7,8}. We have chosen to employ a simple binary mixture as the simplest model to test the assumption that one PAH will not impact the kinetics of another PAH. Phenanthrene is an excellent choice as 1) it is a major component of environmental PAH mixtures^{1-5,9, 2}) it contains a bay region as does BaP and is thus metabolized in a similar fashion¹⁰, 3) it has been evaluated by IARC and EPA and considered not to be a carcinogen (IARC class 3, EPA RPF of 0)^{2,4,6} and 4) it has been previously employed safely in FDA-approved clinical trials in humans at a dose 10,000 ng¹¹. Thus, this will be the first actual test of the RPF approach to risk assessment via micro-dosing in humans of a defined binary mixture of a carcinogenic (BaP) and non-carcinogen (phenanthrene) PAH. For non-cancer risks, the EPA has set a safe lifetime **exposure** value of 40,000 ng/Kg/day⁶, a value more than 2,200 time greater than the single phenanthrene dose (1250 ng/70 Kg) proposed here.

Pharmacokinetic parameters for [14C]-BaP and metabolites, in the presence and absence of co-

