	Previously, the oral exposure slope factor for cancer risk (70 years, 70 Kg adult) for BaP using a linear, non- threshold model (EPA-IRIS) was 7.3 mg/kg-day ⁻¹ , but EPA recently lowered this to 1 mg/(kg-day) ⁴ . Cal/EPA uses a safety factor for age sensitivity (2.9 mg/kg-day ⁻¹). This risk assessment is based on high dose (1-100 mg/kg-day) exposures in rodents- 5-6 orders of magnitude higher doses than human exposures . This risk assessment may not adequately protect some populations. Studies, including our own, with PAH mixtures indicate the linear extrapolated dose may under-estimate actual human risk using the Relative Potency Factor (RPF) approach ⁶ . The RPF approach assumes linear pharmacokinetics for PAHs and their metabolites with dose but this has never been assessed in humans. With the common PAH phenanthrene, a non- carcinogenic PAH, we can test the additivity assumption of the RPF approach in the simplest (binary) mixture possible and at a ratio of the 2 PAHs present in diet.	
	Our preliminary results show the plasma level, as determined by AMS at Crew (highest concentration	

	obtained) after dosing individuals with 46 ng [¹⁴ C]-BaP, was ~ 8 fM (femto(10 ⁻¹⁵ moles/L)) ²⁰ , or 10⁷ lower than an in vitro study (50 nM) showing no adverse impact on hepatocytes. The sensitivity of AMS allows for micro-dosing with [¹⁴ C]-BaP in humans with de minimus risk to determine [¹⁴ C]-BaP and individual metabolites in the low fM range (2-20 femtograms/mL plasma). Our premise is- the best model for humans is humans. Utilizing PBPK models, we can provide a much more accurate estimate of BaP levels in human tissues following exposure at environmental levels as well as individual metabolites representing reduced or enhanced risk.			
1	Background justification should support the objectives of the research as well as the knowledge that is anticipated from the research results. Explain the need for the study and what gap in knowledge the results are expected to fill. Summarize relevant existing data, literature, past and ongoing studies, and how your study ties in with these. Provide specific methods and procedures in a later section.			
4	Is the study student-driven (for the purpose of a thesis, dissertation, or other)?		\boxtimes	
SECTION 14 - Target Enrollment		Yes	No	N/A
1	What is the target enrollment number?			
	Up to 50 people will be enrolled in this study. Our goal is for 7 subjects to complete the study.			

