Blood will be sampled at 0, 0.25 0.5, 1.0, 1.5, 2, 3, 4, 8, 24, and 48 hours (11 draws total, 8-9 of which come from the catheter). The catheter will remain in place for blood draws through hour 4. After the 4-hour blood draw, subjects will have the choice of having the catheter removed and returning for the 8 hour blood draw by straight stick, or they can keep the catheter in place and remain on-site until after the 8 hour blood draw. The subjects will be monitored by the nurse coordinator between IV blood draws. The 8 (possibly), 24, and 48 hour blood draws will be done with straight stick phlebotomy. No more than three (3) skin punctures will be made in an attempt to draw blood at each visit. The first blood draw of each cycle will be 20 mL and then subsequent blood draws will be 10 mL for a total amount of 120 mL (8 tablespoons) per cycle.

Subjects will be instructed to collect all urine during the entire 48-hour study cycle in containers provided by the study team. Subjects will be provided a discrete soft-sided cooler bag to store collected urine samples. They will be instructed to store samples at room temperature between visits and to return any filled containers at their next visit. The longest subjects will need to store samples between visits is 24 hours between Visits 3 and 4.

Two hours after swallowing the capsule, a standardized breakfast will be provided, after which subjects may resume normal eating and drinking. Packaged snacks or juice will be provided prior to the standardized breakfast if the study team determines it is necessary.

This process will be followed for [¹⁴C]-BaP alone and [¹⁴C]-BaP plus phenanthrene for a total of 2 cycles per subject. There will be at least three weeks' washout period between cycles. Previous multiple micro-dosing of the same individual has shown that after 3 weeks there is no detectable [¹⁴C] in plasma or urine, validating the choice of 3 weeks as adequate for a "washout period"^{7,8}. Extending the washout period will not adversely impact the data collected from the subjects but will minimize the subject's exposure to PAHs.

Subjects who have participated in IRB protocol 8233 (Benzo[a]pyrene Ultralow Dose-Response Study) will participate in only the [¹⁴C]-BaP plus phenanthrene cycle if they have complete the 50 ng [¹⁴C]-BaP cycle

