	within the prior 12 months. These subjects will only complete 2 food diaries (3 days prior to the cycle and during the 48-hour cycle). Studies to date have shown little intra-individual variation in [¹⁴ C]-BaP pharmacokinetics with time (at least up to 12 months) between doses. ²⁰		
	Subjects will be asked to defer blood donation for one month before, throughout, and for one month after completion of the study. At any point during the study, subjects will be referred to their physician if the study physician or nurse consider this advisable.		
	Processing of samples:		
	Blood samples will be centrifuged to obtain plasma and peripheral blood mononuclear cells (PBMCs). The [¹⁴ C]-BaP and metabolites will be extracted directly from plasma by liquid/liquid extraction with ethyl acetate. The urine will be pooled over the time periods pre-capsule (baseline), 0 – 12, 12-24, and 24-48 hours. After volumetric quantitation of each pool of urine, 12 mL will be collected, 4 mL will be adjusted to pH 5 and half treated with β -glucuronidase/sulfatase prior to extraction with ethyl acetate. The plasma and urine extracts will be blown down under argon, sealed in amber vials and shipped to LLNL where they will be injected onto an Ultra-Pressure Liquid Chromatograph (UPLC) interfaced via a "moving wire" into the AMS ¹⁹ . We will be able to determine femto(10 ⁻¹⁵)g/mL levels of BaP and BaP metabolites (by co-elution with unlabeled standards available from the OSU Superfund Research Center PAH repository). The time-course of blood and urine levels of parent BaP and metabolites will be used to construct a pharmacokinetic model ¹² . In addition, DNA isolated from PBMCs at 0 hr and 48 hr will be counted directly on the AMS to check for levels of covalent DNA binding.		
0	If the study involves accessing student education records, list all data to be used (e.g. course grades, assignments, GPA, video-recordings of class activities, etc.)		
0	Identify any surveys or questionnaires that are being tested or validated instruments that have been modified for the purposes of this study.		
0	Identify any novel or modified experimental activities that are being tested the purposes of this study.		
0	Specific information related to the use of drugs, devices, biologics, food, biospecimens, and radiation will be requested later in this document.		
2	If any of the activities would be conducted regardless of the research, briefly describe those activities here:	\boxtimes	

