Material storage & preparation: Prior to use, empty Solaray[®] capsules and pharmaceutical grade lactose monohydrate NF (Spectrum Chemical Mfg. #61-1730890) are stored in an airtight bag in a gasket sealed plastic box, in a cabinet in a lab that does not utilize scintillation-detectable radioactivity or human tissues. This box contains all microdosing supplies in an area separated from traditional laboratory supplies.

The [¹⁴C]-BaP is shipped as a concentrated solution (0.10 mCi/ml; specific activity = 26 nCi ¹⁴C/nmol BaP = 0.103 nCi/ng) in toluene. This concentrated solution is stored in sealed containers as received from the supplier at -80°C in a secure carcinogen laboratory in LPSC 383. In order to ensure radiochemical purity (greater than or equal to 98% for the purified concentrated stock) and to prepare a diluted sample suitable for human consumption, the compound is collected as a single peak from an HPLC run. The identity of the compound is confirmed by co-elution with a non-radioactive standard.

Phenanthrene is obtained from the Oregon State University Superfund Core D Chemical Repository and is >99.5% pure as documented by GC-MS/MS.

Two different working stock solutions will be prepared by diluting the 0.10 mCi/mL [¹⁴C]-BaP concentrated solution:

• Stock solution #1 will contain 50 ng [¹⁴C]-BaP /25 μ L = 2 ng/ μ L (5.4 nCi ¹⁴C/25 μ L = 0.2 nCi/ μ L). For example, to make 4 mL of stock solution #1, 8 μ L of the 0.10 mCi/mL solution will be aliquoted into a clean vessel. Toluene is carefully evaporated off, and the [¹⁴C]-BaP aliquot resolubilized into 4 mL 95% food grade ethanol. The radioactivity will be checked with a liquid scintillation counter and

adjusted to the target concentration if needed.

• Stock solution #2 will be prepared in the same manner as stock solution #1 with the addition of 50 ng/ μ L non-radioisotope labeled phenanthrene solubilized in the 95% food grade ethanol for a final concentration of 50 ng [¹⁴C]-BaP + 1250 ng phenanthrene/25 μ L = 5.4 nCi ¹⁴C/25 μ L.

Stock solutions will be aliquoted into clean 2 mL amber glass vials and stored under argon at -80°C. Each stock solution is checked for \ge 95% [¹⁴C]-BaP radioisotope purity on a quarterly schedule throughout the study. Stock solutions will be checked for both purity and concentration on UPLC using UV detection for phenanthrene and BaP and radioisotope detection for [¹⁴C].

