7	For each radioactive material , indicate the activity (mCi) per single dosage, and the total number of dosages per single study and per complete research protocol. A single study is comprised of all dosages received by the participant during a single visit/session.		
7a	Radioactive material name:		

	[7- ¹⁴ C]-benzo[a]pyrene (BaP), specific activity 27 μCi/μmol			
7b	mCi dosage:			
	0.0000054			
7c	Total dose per participant, per study visit:			
	1			
7d	Total exposure per participant, per protocol:			
	2 (or 1- if subject has completed Protocol 8233 within the past 12 months, they will receive only the [¹⁴ C]-BaP plus phenanthrene dose)			
8	Radioactive drug(s) prepared on-site will be prepared, assayed, tested, and labeled in accordance with the FDA's requirements?	\boxtimes		
9	Radioactive drug(s) prepared on-site will be prepared, assayed, tested, and labeled in accordance with an Radioactive Drug Research Committee's (RDRC) requirements?		\boxtimes	
SECTIO	SECTION 29 - Biological Samples		No	N/A
1	Does the study involve the collection or receipt of biological samples?		□ Skip to section 30	
1a	If yes, indicate what biological samples will be received or collected:			
	Urine and venous blood will be collected from subjects during this study.			
2				
	Will samples be obtained prospectively from living individuals?	\boxtimes		
3	Will samples be obtained prospectively from living individuals? Where possible, risks should be minimized by using procedures already being performed on the subjects for diagnostic or treatment purposes. Check all that apply:			
3 3a	 Will samples be obtained prospectively from living individuals? Where possible, risks should be minimized by using procedures already being performed on the subjects for diagnostic or treatment purposes. Check all that apply: Samples are being collected separately from any clinically indicated procedure or another approved study 			
3 3a 3b	 Will samples be obtained prospectively from living individuals? Where possible, risks should be minimized by using procedures already being performed on the subjects for diagnostic or treatment purposes. Check all that apply: Samples are being collected separately from any clinically indicated procedure or another approved study Study involves taking additional samples during clinically indicated procedure or another approved study 			

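### The only cycle order described is BaP alone then mixture, with no randomisation or counterbalancing; if that order is followed, any shift between first and second cycle cannot be separated from the phenanthrene effect

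*Combined protocol and SAP*

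**What the plan says.** - **Order.** Section 13 (Study Overview) has subjects take 50 ng "BaP alone and, following a washout period, previously shown to reduce" plasma and urine levels below detection, and then sets up the comparison with 50 ng BaP plus 1250 ng phenanthrene. Section 20 (Methods and Procedures) says the process is followed for BaP alone and BaP "plus phenanthrene for a total of 2 cycles per subject", at least three weeks apart. It gives no rule for which comes first.
- **Roll-overs.** In Section 20, subjects from protocol 8233 do only the BaP "plus phenanthrene cycle if they have complete the 50 ng" BaP-alone cycle there in the preceding 12 months. Section 28 repeats this: "if subject has completed Protocol 8233 within the past 12 months, they will receive only the" mixture dose. These subjects are always control-first.
- **Support offered.** On washout, Section 20 states: "Previous multiple micro-dosing of the same individual has shown that after 3 weeks there is no detectable" 14C in plasma or urine. On stability, it reports little variation within individuals in BaP "pharmacokinetics with time (at least up to 12 months) between doses", without a figure.
- **Size.** Section 14: "Our goal is for 7 subjects to complete the study".
- **Stocks.** Section 24 prepares a separate stock for each treatment. The mixture stock "will be prepared in the same manner as stock solution #1 with the addition of" phenanthrene.
- **Analysis.** The SAP regresses pharmacokinetic parameters on BaP dose. It contains no mixture-versus-alone comparison and no period term.

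**The concern.** The hypothesis is that phenanthrene leaves BaP metabolites, Cmax and elimination unchanged. With a single order, the within-subject contrast estimates the phenanthrene effect plus whatever else differs systematically between cycles, such as assay session, stock age, diet or season. Such a shift could look like an interaction where there is none, or cancel a real one and appear to confirm no change. The washout evidence concerns residual 14C, which is carry-over; it does not address a shift over time. The plan intends the results for EPA risk models, so the comparison should be free of a confounder that design can remove at low cost.

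**Working it through.** The plan gives no power, variance or drift figure to reproduce. Its only relevant number is 7 completers. The CVs, the shifts and the paired 90% interval below are therefore assumptions.

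**1. Identifiability.** Let d be a subject's log(mixture) minus log(alone), τ the phenanthrene effect and π the shift from first to second cycle. Alone-first subjects have expected d = τ + π; mixture-first subjects have τ − π. With all 7 alone-first, the mean of d estimates τ + π. The design matrix (7 subject effects, period, treatment) has rank 8 of 9, so no analysis separates the two. With a 4:3 split the rank is 9 of 9.

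**2. Effect of a common shift on the 90% interval.** Log SD s = √ln(1+CV²); SE = s√(2/7); noncentrality = ln(1+shift)/SE; coverage from the noncentral t on 6 df. Example: CV 20% gives s = 0.198 and SE = 0.106. A 10% shift then gives noncentrality 0.0953/0.1059 = 0.90 and coverage 79.3%.

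| Common shift | CV 15% | CV 20% | CV 30% | CV 40% |
|---|---|---|---|---|
| 5% | 85.0% | 87.2% | 88.7% | 89.2% |
| 10% | 71.7% | 79.3% | 85.1% | 87.1% |

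A 20% shift at CV 20% gives 54.7%. With a 10% shift, the expected ratio is 1.10 when the truth is 1.00.

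On a testing scale (paired t, two-sided 5%, n = 7, no true effect), shifts of 0.25, 0.5 and 1.0 SD of the paired difference give false rejection in 8.7%, 20.1% and 60.0% of trials.

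**3. Shift in roll-overs only (10%).** The pooled ratio is 1.10^(2/7) = 1.03 with 2 of 7 and 1.10^(3/7) = 1.04 with 3 of 7. Simulated coverage is 88-90% at CV 20-40%. A comparison of roll-overs with in-study subjects would flag the shift in only 5-7% of trials (5% two-sided test).

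**4. Effect and price of counterbalancing.** With a and b subjects in the two orders, the period-adjusted variance is SD_d² × (1/a + 1/b)/4, against SD_d²/7 for the simple paired mean. The width ratio uses the 90% t quantile on the stated df, relative to 1.943 on 6 df.

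| Situation | Variance / SD_d² | df | Relative width |
|---|---|---|---|
| 4:3, no roll-overs | 0.146 | 5 | 1.048 |
| Roll-overs share the shift, 5:2 | 0.175 | 5 | 1.148 |
| Roll-overs share the shift, 6:1 | 0.292 | 5 | 1.482 |
| In-study only, 3:2 (2 roll-overs dropped) | 0.208 | 3 | 1.463 |
| In-study only, 2:2 (3 roll-overs dropped) | 0.250 | 2 | 1.988 |

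If roll-overs are assumed free of any shift, the all-completer ratio is 1.052 (3:2 plus 2) or 1.037 (2:2 plus 3). Without a period term, 4:3 still reduces the bias to (4−3)/7 = 1/7 of the shift: 1.10^(1/7) = 1.014.

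**5. Phenanthrene washout if mixture comes first.** Using the dietary figures in Sections 13 and 37, the extremes are 1250/(21 × 9350) = 0.6% and 1250/(21 × (4250 − 1350)) = 2.1% of intake over a 21-day washout.

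**The case against.** **The order is inferred.** Section 13 is an overview, and the operative text in Sections 20 and 24 names the two capsules without a sequence. Part of Section 20, after the methods answer, is missing from the public text. A reader might infer that the plan mandates one order for everyone. The documents do not say that: for new subjects the order is unstated, and it is fixed only for roll-overs. This stands, and it is why the point is conditional.

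**Shifts are partly measured and limited.** Each cycle has food diaries before and during dosing and a pre-dose plasma panel of BaP and 62 other PAHs, so dietary shifts can be examined. A claim that the data could reveal nothing about a shift's source would go too far. Capsules are released by batch, and stocks are checked for purity and concentration. At most two subjects are dosed per week, so calendar step changes need not line up with cycle number, and nothing ties an assay session to a cycle. All of this stands. None of it separates a remaining common shift from treatment.

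**The roll-overs' old control looks worse than it is.** A reader might infer that a control up to 12 months old ruins the comparison. The stability statement concerns separate doses, so it may already include batch and assay variation. A between-study shift is inseparable from treatment only if all 7 completers are roll-overs. The statement has no figure, however, so it cannot be relied on fully.

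**The remedy is partial.** Roll-overs cannot be counterbalanced, and each treatment keeps its own stock. Control-first also avoids any phenanthrene carry-over. These limits are real.

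**Conclusion.** The point holds in conditional form and should be fixed. If BaP alone always comes first, period and treatment are fully aliased; this follows from the design and needs no numerical assumption. How much harm results is unknown, because the documents give no within-subject CV, no drift and no roll-over count. On the assumed paired interval the loss is small for a 5% shift, moderate for 10% and serious for 20% at a low CV. The documents do not support concluding that the result is in fact biased, or that a shift of any given size is likely. They support only that a shift, if present, could not be distinguished from phenanthrene. Confidence is medium, because the order for new subjects rests on one overview sentence.

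**What to change.** 1. State the cycle order in Section 20.
2. Randomise or counterbalance it for subjects who take both cycles in this study.
3. Specify the mixture-versus-alone comparison in the SAP, which has none at present, and include a period term.
4. Analyse each in-study subject's two cycles in the same AMS session where possible.
5. Identify the 8233 roll-overs and pre-specify the result with and without them as a sensitivity analysis.
6. The SAP is written in the past tense. If cycles are already complete, report the actual order and state period confounding as a limitation.

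**Cost.** A short amendment and an allocation list, with no extra subjects or visits. Precision costs are in the second table above; the in-study-only interval is 46-99% wider with 2-3 roll-overs, so it can serve only as a sensitivity result. A batch serves up to two subjects, so without roll-overs 7 subjects need at least 4 + 4 = 8 batches under either plan, provided subjects dosed in the same week share an order. If no doses share a batch, 14 are needed. That is 0 to 6 extra batches, each with 3 quality-control capsules (0 to 18). Mixture-first relies on a phenanthrene washout that the protocol does not document, although the dietary figures suggest that carry-over is small.

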administration with phenanthrene, will be assessed by ULPC-AMS in plasma and urine collected over 48 hours. Metabolite profiles and kinetics of elimination over this dose range are predicted to be consistent with the BaP PBPK model developed by our present and past collaborators at Pacific Northwest National Laboratory (PNNL)¹². The results from this study will be disseminated in peer-reviewed toxicology/environmental health journals, at scientific meetings and provided to the U.S. EPA for incorporation into their risk assessment models. The experimental procedure employs accelerator mass spectrometry (AMS) for analysis. AMS (10³-10⁹ more sensitive for ¹⁴C than scintillation counting) is increasingly used to determine pharmacokinetics of drugs under development. A dose given to human volunteers of no more than 1/100 the expected therapeutic dose, or less than 100 µg of [¹⁴C]-labeled drug (usually 100-200 nCi), is referred to as "microdosing" (Phase 0 studies or eIND studies). This approach has been validated for exploratory clinical development by the Consortium for Resourcing and Evaluating AMS Microdosing (CREAM Trial) and the EU Microdosing AMS Partnership Programme (EUMAPP). This early use of human subjects in drug development is consistent with the goals of the FDA Critical Path Initiative and AMS in exploratory IND applications has been addressed by FDA¹³. AMS has been used in toxicology and carcinogenesis studies. AMS sensitivity allows the study of pharmacokinetics and DNA binding of environmental contaminants known to be animal carcinogens and suspected of being human carcinogens including the cooked meat mutagens PhIP and MeIQx, the mycotoxin and human hepatocarcinogen AFB₁, in addition to BaP¹⁴. It is noteworthy that our group has successfully completed AMS studies with AFB₁ and the PAH, dibenzo[def,p]chrysene (DBC)^{7,8,15}. IARC estimates that a non-smoker, not exposed occupationally, will receive a daily dose of 270-700 ng of BaP; about 95% through the diet². The European Union maximum limit for BaP in fish is 2,000 ng/Kg f.w. and the FDA Limit of Concern (LOC) is 35,000 ng/Kg. The dose of 50 ng would be the equivalent of eating 25 or 1.4 g of fish at the EU, and FDA limits, respectively. The World Health Organization has set an estimated safe daily lifetime (70 years for a 70 Kg individual, cancer endpoint) exposure to BaP of 42-350 ng⁹. With respect to the internal dose of [¹⁴C] of 5.4 nCi, this represents 0.6% the dose given in a common diagnostic procedure (¹⁴C-urea test for Helicobacter)¹⁶ and 4 and 5 orders of magnitude lower than a recently published paper dosing people with 300 μ Ci of epicatechin¹⁷. Therefore, from the standpoint of both chemical and radioisotope dose to the volunteers, this protocol represents de minimus risk and that was the finding of the FDA (IND 117175) in a "study may proceed" determination for our IRB protocol 5644 which uses a dose of 46 ng (5 nCi).

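### Is the preliminary plasma peak (~8 fM, about 2 fg/mL) too close to the assay's stated range for a fall in Cmax to be seen?

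*Combined protocol and SAP*

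**What the plan says.** Section 13 item 1 states a hypothesis of no change in plasma and urine metabolites, in the labelled BaP "Cmax in blood or the rate of elimination" when phenanthrene is added. It also says that the washout brings "levels in plasma and urine to levels below detection (<1 fg/mL"). Pharmacokinetic parameters "will be assessed by ULPC-AMS in plasma and urine collected over 48 hours".

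Section 13 item 3 (background justification) gives a plasma level at Cmax of about 8 fM "after dosing individuals with 46 ng", and sets it against an in vitro "study (50 nM) showing no adverse impact on hepatocytes", said to be 10^7 higher. The next sentence says that AMS can determine BaP and "individual metabolites in the low fM range (2-20 femtograms/mL plasma").

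Section 20 (Processing of samples) says that the laboratory can determine femtogram-per-mL "levels of BaP and BaP metabolites (by co-elution with unlabeled standards"), and that blood and urine levels of parent and metabolites over time will feed a pharmacokinetic model. Section 14 says "Our goal is for 7 subjects to complete the study".

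Neither the protocol nor the Statistical Analysis Plan (SAP) gives a limit of quantification, a rule for values below it, or a statement of whether 8 fM is parent BaP or total 14C.

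**The concern.** The peak is given in fM and the range in fg/mL, so the mismatch shows only after conversion. The peak then lies at the lowest value of the range that the next sentence describes, and at about twice the detection level.

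For a hypothesis of no change, a floor close to the peak acts in one direction: falls would drop out of the data and rises would stay. Seven completers leave little to spare. The rate of elimination looks more exposed still, because a concentration that starts at twice the detection level can be followed down for only about one half-life.

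**Working it through.** **Inputs.** Peak 8 fM at 46 ng, and range 2-20 fg/mL (Section 13 item 3). Dose 50 ng and detection level 1 fg/mL (Section 13 item 1). Formula C20H12 (Section 24 item 6), so the molecular weight is 252.3. As a cross-check, Section 24 item 17 gives 26 nCi/nmol and 0.103 nCi/ng, and 26/0.103 = 252.4 ng/nmol.

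**The plan's own figure.** 50 nM / 8 fM = 50e-9 / 8e-15 = 6.25e6 = 10^6.8. This agrees with the stated 10^7 to an order of magnitude, so a misprint of the fM unit is unlikely.

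**Conversion** (fg/mL = fM × 252.3 / 1000).
- Peak at 46 ng: 8 fM = 2.02 fg/mL. If about 8 means 7.5 to 8.5 fM, it is 1.89 to 2.14 fg/mL.
- Scaled to 50 ng (proportionality assumed): 2.02 × 50/46 = 2.19 fg/mL.
- 2 and 20 fg/mL = 7.9 and 79 fM; 1 fg/mL = 4.0 fM.
- If 2-20 fM was meant: 0.50 to 5.0 fg/mL.

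**Room below a peak of 2.19 fg/mL.** Largest fall that stays measurable = 1 − floor/2.19. Half-lives that can be followed = log2(2.19/floor).

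| Assumed floor (fg/mL) | Largest fall | Half-lives |
|---|---|---|
| 2 | 9% | 0.13 |
| 1 | 54% | 1.13 |
| 0.5 | 77% | 2.12 |

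At the unscaled 2.02 fg/mL, the first two rows become 0.9% and 0.01, and 50% and 1.01.

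**Complete pairs among 7 subjects.** Simulated lognormal peaks with median 2.19. The documents give no variability, so a between-subject CV of 20-40% and a within-subject CV of 10-20% are assumed. A pair counts if both peaks are at or above the floor.

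| Floor (fg/mL) | No change | True 30% fall | True 30% rise |
|---|---|---|---|
| 2 | 3.3-4.0 | 0.8-1.8 | 3.9-4.6 |
| 1 | 6.6-7.0 | 5.9-6.8 | 6.7-7.0 |
| 0.5 | 7.0 | 7.0 | 7.0 |

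**What that count leaves out.** At a floor of 2 fg/mL with a 30% fall, 74-96% of simulated studies have fewer than 3 complete pairs. Yet a subject who is measurable on BaP alone and below the limit on the mixture is evidence of a fall. The expected number measurable on BaP alone is 7 × Φ(ln(2.19/2)/s), where s is the total log SD.
- CVs 20% and 10%: s = 0.22, which gives 4.6. Less 0.8 complete pairs, 3.8 pairs point down.
- CVs 40% and 20%: s = 0.43, which gives 4.1. Less 1.8, 2.3 pairs point down.

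In the same simulation, pairs measurable only on the mixture average 0.14 or fewer. Kept as left-censored values, the one-sided pairs show the fall even at this floor.

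**Can the three figures coexist?** Yes: detection at 1, a parent peak at about 2.0, and a span of 2 to 20 for parent and individual metabolites, some of them higher than parent.

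**The case for a change.** The strongest case for a change is that the documents allow three lower ends (2, 1 or 0.5 fg/mL) and the consequences differ sharply. At 2, a parent Cmax comparison is nearly one-sided. At 1, Cmax is safe but about one half-life of plasma parent is thin support for a claim about elimination. At 0.5, neither is a serious problem. The correction would be text only, and the cited 46 ng results should hold the figures.

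Part of this stands. Low fM is a loose label for 7.9-79 fM, and a stated quantification limit would help the reader. Plasma parent BaP alone would indeed be weak evidence on elimination.

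There is also an unresolved reading. If 8 fM is total 14C, parent BaP lies lower by an amount that the documents do not give. One compound would then need 91-99% of all 14C to reach 2 fg/mL (2/2.19 and 2/2.02). That share assumes the mass of BaP; for a diol-epoxide of mass 302.3 it is 76-83%. This reading would make the printed range a poor description of individual metabolites, but it still does not make 2 fg/mL a limit.

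The rest does not stand. The 2 fg/mL floor comes from background text on what the assay can reach, and the only level tied to detection is 1 fg/mL. A recommendation built on three possible floors also fixes nothing definite. At 0.5 nothing changes. At 1 it largely repeats the joint blood-and-urine model already planned in Section 20. At 2 it would move the judgement to urine and metabolites, for which no limits are given either.

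**Conclusion.** The conversions are right, but the conclusion that a fall in Cmax could not be seen is not supported. With the stated detection level as the limit, parent Cmax can fall by about 50-54% and still be measured, and a true 30% fall leaves 5.9 to 6.8 of 7 complete pairs. The limited view of plasma elimination (1.0 to 1.1 half-lives) is real for parent BaP in plasma, but the plan does not rest on that quantity alone.

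What remains is a loose unit label and an unstated limit. Analysts will take the limit from the assay record, work in one unit, and treat values below it as left-censored rather than drop them. None of this needs a different design, sample or endpoint.

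The conclusion assumes that 8 fM refers to parent BaP, that the peak scales in proportion from 46 to 50 ng, and that variability lies in the assumed ranges. How well urine and metabolite data support the elimination comparison cannot be derived from the documents.
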